4.1. Study Hypothesis

The primary hypothesis is that study subjects who received the FlareHawk expandable cage(s) through a TLIF or PLIF procedure experienced fusion by 12 months (+/- 3 mo) follow-up, with improvements in clinical outcomes related to pain and/or disability compared to pre-operative scores. Further, the subjects are hypothesized to have not experienced any unforeseen device- or procedure-related adverse events

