The intensity of the adverse event will be determined by the investigator using the following definitions established by the World Health Organization and not necessarily the subject's interpretation:

None: patient outcome is not symptomatic, or no symptoms detected and no treatment is required.

Mild: patient outcome is symptomatic, symptoms are mild, loss of function or harm is minimal or intermediate but short term, and no or minimal intervention (e.g., extra observation, investigation, review or minor treatment) is required.

Moderate: patient outcome is symptomatic, requiring intervention (e.g., additional operative procedure; additional therapeutic treatment), an increased length of stay, or causing permanent or long-term harm or loss of function.

Severe: patient outcome is symptomatic, requiring life-saving intervention or major surgical/medical intervention, shortening life expectancy or causing major permanent or long-term harm or loss of function

Death: on balance of probabilities, death was caused or brought forward in the short term by the incident.

The relationship of the AE to the implant or surgical procedure is determined according to the following definitions:

Device related: The AE can be reasonably associated with the presence or performance of the device and follows a reasonable temporal sequence to the device implant

Procedure related: The AE has been established as a potential risk or complication associated with any type of spinal surgical procedure and not specific to the receipt of the device.

Not related: The AE has no temporal sequence from the receipt of the device or it can be explained by other factors, including underlying disease, concomitant medication or concurrent treatment. This also includes events associated with general surgical procedures (e.g. anesthesia reactions).

5.1 Subject Safety:

The expandable cage used in this study is currently used in standard of care procedures for these lumbar spine disorders. No experimental devices or products were used in this study and all patients were treated according to the standard practices of the study investigators.

5.2 Mitigation of Risks:

This is a retrospective chart review that does not introduce any additional risks to the patient.

6. Image and Data Analysis

6.1 Radiographic Fusion Assessment:

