For any adverse events, the observed rate of each type of event will be summarized as a percentage with the 95% confidence interval and compared with rates observed in the literature describing the current state of the art with other PLIF and TLIF interbody cages.

7. Ethical and Regulatory Requirements:

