3	My sex life is severely restricted by pain
4	My sex life is nearly absent because of pain
5	Pain prevents any sex life at all

Section 9 – Social Life	
0	My social life is normal and gives me no extra pain
1	My social life is normal but increases the degree of pain
2	Pain has no significant effect on my social life apart from limiting my more energetic interests e.g. sports
3	Pain has restricted my social life and I do not go out as often
4	Pain has restricted my social life to my home
5	I have no social life because of pain

Section 10 – Traveling	
0	I can travel anywhere without pain
1	I can travel anywhere but it gives me extra pain
2	Pain is bad but I manage journeys over two hours
3	Pain restricts me to journeys of less than one hour
4	Pain restricts me to short necessary journeys under 30 minutes
5	Pain prevents me from traveling except to receive treatment

Clinical Site Number:

Subject Number:

Case Report Form
Integrity Implants FlareHawk® Study
Follow-up Visit – VAS Score

Page 1 of 1

FOLLOW-UP VISIT

DATE OF VISIT: / /
MM DD YYYY

VISUAL ANALOG SCALE (VAS)

Please enter the VAS score as documented at the follow-up visit in the medical records for the level of **RIGHT LEG** pain.

VAS **Right Leg** Pain Score: _____ Not Recorded

Please enter the VAS score as documented at the follow-up visit in the medical records for the level of **LEFT LEG** pain.

VAS **Left Leg** Pain Score: _____ Not Recorded

Please enter the VAS score as documented at the follow-up visit in the medical records for the level of **BACK** pain.

VAS **Back Pain** Score: _____ Not Recorded

Clinical Site Number:

Subject Number:

Case Report Form
Integrity Implants FlareHawk® Study
 Intra-Operative Adverse Event Log

INTRA-OPERATIVE ADVERSE EVENT (AE) LOG			No AEs Recorded 			
If Adverse Events have occurred, check “yes” or “no” for each event listed below. If “yes” is marked for an Adverse Event below, please complete all of the columns to the right.						
Adverse Events	Yes / No		Severity	Relatedness	Action Taken	Outcomes
			1- None 2- Mild 3- Moderate 4- Severe 5- Death	1- Device related 2- Procedure related 3- Not related	1- None 2- Medication/Therapy 3- Revision Surgery 4- Additional Surgery 5- Other	1- Resolved 2- Ongoing at 12-month (+/- 3 month) Follow-up 3- Unknown
Device component breakage/fracture	Yes 	No 				
Device malfunction	Yes 	No 				

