Please complete all columns below if additional Adverse Events are recorded.

Other Adverse Events (Describe event below)	Onset Date MM/DD/YYYY	Resolution Date MM/DD/YYYY	Severity 1- None 2- Mild 3- Moderate 4- Severe 5- Death	Relatedness 1- Device related 2- Procedure related 3- Not related	Action Taken 1- None 2- Medication/ Therapy 3- Revision Surgery 4- Additional Surgery 5- Other	Outcomes 1- Resolved 2- Ongoing at 12-month (+/- 3 month) Follow-up 3- Unknown
	/ /	/ /				
	/ /	/ /				
	/ /	/ /				
	/ /	/ /				
	/ /	/ /				

Clinical Site Number: Subject Number:

Case Report Form
Integrity Implants FlareHawk® Study
Radiographic Reviewer

CRF TO BE COMPLETED BY RADIOGRAPHIC REVIEWER ONLYDATE OF X-RAY: / /
MM DD YYYY**RADIOGRAPHS**X-ray views evaluated (check all that apply): AP Lateral Flexion/Extension **RADIOGRAPHS**

Using the Bridwell-Lenke grading system, what is the X-ray fusion status at L2 - L3?	Grade 1	
	Grade 2	
	Grade 3	
	Grade 4	
NA – Subject not implanted with FlareHawk device at L2-L3		

Using the Bridwell-Lenke grading system, what is the X-ray fusion status at L3 – L4?	Grade 1	
	Grade 2	
	Grade 3	
	Grade 4	
NA – Subject not implanted with FlareHawk device at L3-L4		

Using the Bridwell-Lenke grading system, what is the X-ray fusion status at L4 – L5?	Grade 1	
	Grade 2	
	Grade 3	
	Grade 4	
NA – Subject not implanted with FlareHawk device at L4-L5		

Using the Bridwell-Lenke grading system, what is the X-ray fusion status at L5- S1?	Grade 1	
	Grade 2	
	Grade 3	
	Grade 4	
NA – Subject not implanted with FlareHawk device at L5-S1		

Was any magnification adjustment used by the radiographic reviewer to grade fusion status? Yes No

If "Yes", describe below: _____

APPROVAL

Reviewer Signature: _____

Date: _____

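### 'Procedure related' is defined by prior knowledge of the risk, so the procedure half of the 'no unforeseen events' hypothesis is met by definition, and no count of unforeseen events is planned for either half

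*Combined protocol and SAP*

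**What the plan says.** The safety limb of the hypothesis stands in section 4.1 of the clinical protocol and again in Attachment A section 3.1: "the subjects are hypothesized to have not experienced any unforeseen device- or procedure-related adverse events". Neither place defines 'unforeseen'.

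Attachment A section 5 gives three relationship categories:

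- 'Procedure related' has this condition: "The AE has been established as a potential risk or complication associated with any type of spinal surgical procedure". A further clause says that the event must not be particular to having received the cage.
- 'Device related' has this one: "The AE can be reasonably associated with the presence or performance of the device and follows a reasonable temporal sequence to the device implant".
- 'Not related': no temporal sequence, or explained by other factors. The definition adds: "This also includes events associated with general surgical procedures (e.g. anesthesia reactions").

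The intra-operative and post-operative adverse event logs in the case report form offer only these codes: "1- Device related 2- Procedure related 3- Not related". Their other columns are severity, action taken and outcome, with onset and resolution dates on the post-operative log. Neither log has a column for whether an event was anticipated. Both have free-text rows for unlisted events, and the post-operative log instructs the site: "Please complete all columns below if additional Adverse Events are recorded".

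For the analysis, section 9.2 of the clinical protocol and Attachment A section 6.2 say that "the observed rate of each type of event will be summarized as a percentage with the 95% confidence interval" and that the rates will be compared with published rates for other PLIF and TLIF cages.

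**The concern.** The hypothesis asks whether anything happened, attributable to the device or the operation, that nobody had anticipated. The 'Procedure related' code asks something else: whether the event is already a recognized hazard of spinal surgery. An event that passes the second test is foreseen in the ordinary sense of the word. The events the hypothesis is meant to find are therefore kept out of the category in which it looks for them.

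Device performance and safety are the stated purpose of the study, and adverse events are a secondary outcome. A final report could say truthfully that no unforeseen procedure-related events were seen, and the sentence would carry no information. For device-related events the statement could carry information, but the plan does not say how it would be derived. If the list of foreseen events were chosen after the events were known, the result would be post hoc.

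**Working it through.** **1. The three definitions side by side**

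| Code | Requires association or timing? | Requires that the risk be already known? |
|---|---|---|
| Device related | Yes, both | No |
| Procedure related | Neither is stated | Yes |
| Not related | No temporal sequence, or another explanation; also general surgical events | No |

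Only 'Procedure related' turns on prior knowledge.

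**2. A novel procedural event followed through the form.** Take an event caused by the TLIF or PLIF procedure, not by the cage, and not previously recognized as a risk of spinal surgery.

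- 'Procedure related' is closed to it, because the risk is not established.
- The log leaves 'Device related', which blames the cage, or 'Not related', which takes the event out of the hypothesis.
- Either way the attribution is wrong. Once the event is on the log, its type still receives a rate and interval, because sections 9.2 and 6.2 do not filter by relatedness.

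On the ordinary meaning of 'unforeseen', the set of events that are both coded 'Procedure related' and unforeseen is empty, at any sample size.

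**3. A novel device event followed through the form.** 'Device related' is open to it. If unlisted, it goes in a free-text row with a description and a relatedness code. Its foreseen status could then be derived centrally against a list. The text supplied names no list for this purpose, no assessor and no table. CER-00001 Rev C is cited for anticipated adverse events, but only in the sample size sections (6.1 and Attachment A 3.6).

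**4. The plan's own safety figure.** Those sections state that 100 subjects allow likely detection of events with probability 1.6% or more at 80% power. The chance of at least one event is 1 − (1 − 0.016)^100 = 0.8007, and the inverse is 1 − 0.2^(1/100) = 1.597%. The figure reproduces. It concerns seeing an event at all, not classifying it as foreseen.

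**5. What a zero count would mean under a usable definition.** With 0 of 100 patients:

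- Exact two-sided 95% upper limit: 1 − 0.025^(1/100) = 3.62%.
- Wilson upper limit, with z² = 3.8415: 3.8415 / (100 + 3.8415) = 3.70%.
- If the true rate were 1%, the chance of seeing none would be 0.99^100 = 36.6%.

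These figures apply to any zero count in 100. They show why the count needs an interval and are not a measure of the coding problem.

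**The case against.** The strongest reply is that 'unforeseen' is undefined, so the circularity depends on how the word is read. If it meant absent from CER-00001, or unexpected in severity or frequency, an established spinal risk could be both 'Procedure related' and unforeseen. This is fair, and it limits the claim to the ordinary meaning. But the documents state no such alternative, and adopting one would not turn the definition into a causal one.

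A second reply is that the data exist and the sentence is descriptive, with no formal test planned. For the device half, the data point stands. A reader might infer that the whole safety hypothesis is untestable, or that the device half has no data item. The documents do not support that: 'Device related' is not confined to known risks, and unlisted events are described and coded.

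Two further inferences also fail:

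- A reader might infer that a known risk of TLIF or PLIF in particular has no code, because the definition speaks of any type of spinal procedure. The natural sense is 'whichever type', which includes TLIF and PLIF.
- A reader might infer that events coded 'Not related' vanish from the report. The planned rates are by event type whatever the relatedness code, so what suffers is attribution.

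It is also true that rewording 'Procedure related' alone would be incomplete. 'Not related' expressly takes in general surgical events such as anesthesia reactions, so an event attributable to the index operation could then fit two codes.

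**Conclusion.** The point holds in two parts of unequal strength.

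- **Procedure half:** met by definition on the ordinary meaning of 'unforeseen', and so uninformative. Novel procedural events are misattributed on the log.
- **Device half:** assessable from the existing logs, but with no pre-specified definition, reference list or count.

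The size is qualitative: one stated safety claim cannot be supported as written. The primary fusion analysis, the VAS and ODI analyses and the event-type rates are unaffected. The change should be made, but it does not threaten the study's main results.

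The conclusion assumes the ordinary meaning of 'unforeseen', and that no definition of it sits in the parts of the file not available here (between the heading of section 8 and section 9.1 of the clinical protocol, around the approval pages, and next to the site list). The adverse event definitions, the logs and the analysis text are all present.

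**What to change.** 1. In Attachment A section 5, define 'Procedure related' as reasonably attributable, causally and temporally, to the index TLIF or PLIF procedure and not to the device, whether or not the risk is already known. Reconcile this with the 'Not related' sentence on general surgical events, so that no event fits two codes.
2. Classify each related event as foreseen or unforeseen against a list fixed before data review: the events in Attachment A section 4.3 plus the labeling and the CER-00001 version in force. This can be derived centrally from the existing logs or recorded in one added column.
3. In section 9.2 and Attachment A section 6.2, report the number of patients with at least one unforeseen device- or procedure-related event, with its 95% interval. If the count is 0 of 100, state the upper limit (about 3.6% exact, 3.7% Wilson) beside it.

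The cost is one reworded definition with its neighbor reconciled, one central classification or form column, and one table row. No new patients or procedures are needed. The downside is that some events now coded 'Not related' or 'Device related' will count as procedure related.

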1.2 Device Description

The Integrity Implants FlareHawk Interbody Fusion System is an expandable lumbar intervertebral body fusion device intended for use in the lumbosacral spine from L2-S1 and is intended for intervertebral lumbar fusion. The FlareHawk implant consists of a Shell and a Shim component that are offered in a range of sizes to accommodate variation in patient anatomy. The Shell component is a rectangular frame with struts on all four sides that allow for insertion into the intervertebral body space in a non-expanded form, and subsequent expansion following the insertion of the Shim component. The Shim component has a tapered front end that inserts into and expands the Shell component to the desired vertical and horizontal dimensions. When fully inserted, the Shim locks within the Shell to provide structural stability for interbody fusion. An integrated “Core” in the Shell serves to anchor the delivery instrument during Shim insertion. Protrusions on the superior and inferior surfaces of the implant grip the adjacent vertebral endplates to resist expulsion. The FlareHawk implant is to be filled with autogenous and/or allogenic bone graft composed of cancellous and/or corticocancellous bone. Once implanted, the FlareHawk

implant is designed to restore intervertebral disc height, provide anterior column support and maintain structural stability of the motion segment to facilitate intervertebral body fusion.

2. Purpose of the Study:

The purpose of this study is to evaluate the clinical outcomes of patients who have undergone a TLIF or PLIF procedure with a FlareHawk expandable interbody fusion cage(s) to assess the device's performance and safety when used in accordance with its intended use.

3. Study Design

3.1 Study Hypothesis:

The primary hypothesis is that study subjects who received the FlareHawk expandable cage(s) through a TLIF or PLIF procedure experienced fusion by 12 months (+/- 3 mo) follow-up, with improvements in clinical outcomes related to pain and/or disability compared to pre-operative scores. Further, the subjects are hypothesized to have not experienced any unforeseen device- or procedure-related adverse events.

3.2 Study Description:

This is a retrospective clinical study (chart review) of patients who have previously undergone TLIF or PLIF surgery with the FlareHawk expandable interbody fusion cage at one or two contiguous levels.

3.3 Primary Outcome:

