Radiographs will be evaluated by up to three reviewers (two primary reviewers and an adjudicator, as necessary, to evaluate any contradicting reviews by the primary reviewers). Reviewers will be 3rd party board-certified orthopedic surgeons, neurosurgeons, or radiologists.

Fusion status will be determined according to the Bridwell-Lenke grading system [Bridwell and Lenke et al, 1995], with grades 1-2 accepted as “Fused” and grades 3-4 accepted as “Not Fused”:

- Grade 1: Fused with remodeling and trabeculae present
- Grade 2: Graft intact, not fully remodeled and incorporated, but no lucency present
- Grade 3: Graft intact, potential lucency present at top and bottom of graft
- Grade 4: Fusion absent with collapse/resorption of the graft

6.2 Data Analysis:

Primary outcome:

The proportion of levels achieving arthrodesis at 12 months (+/- 3 months) will be summarized as a percentage and 95% confidence interval, based on the Wilson score method for binomial confidence intervals.

Secondary outcomes:

Continuous variables, such as baseline demographics and change in patient-reported outcomes from preoperative baseline to 12 months, will be summarized using mean, standard deviation, minimum and maximum values. Paired t-test or a non-parametric equivalent (if data does not satisfy assumptions of normality) will be used to determine if changes in VAS or ODI scores are statistically significant from preoperative baseline to 12 months (+/- 3 months) follow-up. Responder analyses for changes in patient-reported outcomes at 12 months (+/- 3 months) will be conducted using minimum clinically important differences (MCID). Significant clinical improvements from preoperative baseline to 12 months (+/- 3 months) follow-up will be determined on a per-patient basis using the following MCID values:

- Improvement in ODI \geq 10 points [Ostelo et al. 2008]
- Improvement in VAS leg pain \geq 15 points [Ostelo et al. 2008]
- Improvement in VAS back pain \geq 15 points [Ostelo et al. 2008]

The proportion of patients with improvements exceeding the MCID values will be summarized as a percentage and 95% confidence interval.

Sub-group analyses will be performed based on the implant version (split-shim vs. “Version B”), history of previous surgery at the index level, patient co-morbidities, and demographic variables.

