Dural tear/injury	Yes 	No 				
Nerve root injury	Yes 	No 				
Other Adverse Events (Describe event below)			Severity	Relatedness	Action Taken	Outcomes

Clinical Site Number:

Subject Number:

Case Report Form
Integrity Implants FlareHawk® Study
 Post-Operative Adverse Event Log

POST-OPERATIVE ADVERSE EVENT (AE) LOG **No AEs Recorded**

If Adverse Events have occurred, check “yes” or “no” for each event listed below. If “yes” is marked for an Adverse Event below, please complete all of the columns to the right.

Adverse Events	Yes / No		Onset Date	Resolution Date	Severity	Relatedness	Action Taken	Outcomes
			MM/DD/YYYY	MM/DD/YYYY	1- None 2- Mild 3- Moderate 4- Severe 5- Death	1- Device related 2- Procedure related 3- Not related	1- None 2- Medication/ Therapy 3- Revision Surgery 4- Additional Surgery 5- Other	1- Resolved 2- Ongoing at 12-month (+/- 3 month) Follow-up 3- Unknown
Infection	Yes 	No 	/ /	/ /				
Donor site pain	Yes 	No 	/ /	/ /				
Complex regional pain syndrome	Yes 	No 	/ /	/ /				
Urinary retention/difficulty	Yes 	No 	/ /	/ /				
Ipsilateral or contralateral radiculopathy	Yes 	No 	/ /	/ /				
Device component breakage/fracture	Yes 	No 	/ /	/ /				
Device or device component migration/retropulsion	Yes 	No 	/ /	/ /				
Device complication (e.g. loss of expansion)	Yes 	No 	/ /	/ /				
Device subsidence	Yes 	No 	/ /	/ /				
Loss of fixation	Yes 	No 	/ /	/ /				
Non-union	Yes 	No 	/ /	/ /				
Vertebral fracture	Yes 	No 	/ /	/ /				
Adjacent segment disease	Yes 	No 	/ /	/ /				

Clinical Site Number:

Subject Number:

Case Report Form
Integrity Implants FlareHawk® Study
 Post-Operative Adverse Event Log

POST-OPERATIVE ADVERSE EVENT (AE) LOG Continued

No AEs Recorded

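### The MCID responder rule takes no account of re-operation before the 12-month score, so the responder rate credited to the index device can be inflated

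*Combined protocol and SAP*

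**What the plan says.** Section 9.2 and Attachment A section 6.2 carry the same text. They announce the responder analysis ("Responder analyses for changes in patient-reported outcomes at 12 months (+/- 3 months) will be conducted using minimum clinically important differences (MCID") and settle each patient's status by score change: "Significant clinical improvements from preoperative baseline to 12 months (+/- 3 months) follow-up will be determined on a per-patient basis using the following MCID values". The thresholds are 10 points for ODI and 15 points each for VAS leg and VAS back. The summary is then "The proportion of patients with improvements exceeding the MCID values will be summarized as a percentage and 95% confidence interval". The same two sections plan a paired t-test, or a non-parametric test, on the change from preoperative baseline to 12 (+/- 3) months.

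The Visit 3 case report form takes the scores charted at the follow-up visit. It sets no condition on what happened between the index operation and that visit.

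Re-operation is foreseen as an event. The Post-Operative Adverse Event Log lists under action taken: "3- Revision Surgery 4- Additional Surgery". The only planned use of adverse event data, however, is a rate per event type, compared with the literature. Re-operation is not among the subgroup factors. The one exclusion criterion about other spinal surgery concerns fusion at the study level before the index procedure.

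**The concern.** The stated purpose (section 1.1 and Attachment A section 2) is to assess the performance and safety of the device. The hypothesis (section 4.1 and Attachment A section 3.1) is that patients who received it fused "with improvements in clinical outcomes related to pain and/or disability compared to pre-operative scores". A second lumbar operation is itself a treatment for pain and disability. Take a patient re-operated at month 5 for radiculopathy or migration who is 20 ODI points better than preoperative baseline at month 12. The written rule makes this patient an ODI responder. The event appears in the adverse event table and the improvement in the responder table, and nothing in the report would connect the two.

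With no control arm, there is no comparison group in which the effect of later surgery would also show. A reader of the responder rate could not tell how many of the improvements came after a second operation.

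**Working it through.** **Step 1. The plan's own figures.** The VAS, ODI and responder outcomes have no sample-size or power statement, so no stated figure depends on how re-operation is handled. The nearest check is the sample size section (section 6 and Attachment A section 3.6), which gives 80.2%-93.0% for 88 of 100. The Wilson interval is

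[p + z²/2n ± z·√(p(1−p)/n + z²/4n²)] / (1 + z²/n), with z = 1.96, so z² = 3.8416.

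For p = 0.88 and n = 100:
- centre = (0.88 + 0.019208)/1.038416 = 0.8659
- half-width = 1.96·√(0.001056 + 0.000096)/1.038416 = 0.0641
- interval = 80.2%-93.0%, which reproduces the plan.

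The target of 118 also reproduces: 100/0.85 = 117.6, rounded up.

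**Step 2. Direction for the responder rate.** Let R be the number of patients meeting the MCID threshold, and r the number of those who were re-operated before the 12-month score. The written rule gives R/n. Counting re-operation as non-response gives (R − r)/n. Because r ≥ 0, the written rule can never give the lower figure. The gap is r/n, which is one percentage point per re-operated responder when n = 100, whatever R is.

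**Step 3. Size, on assumed values.** The documents give neither a re-operation rate nor an expected responder rate. Assume n = 100 with paired scores and R = 75. The plan does not name an interval method for the responder proportions, so I use Wilson, which it names for the primary outcome.

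| Re-operated responders (r) | Rate with these as non-responders | Wilson 95% CI |
|---|---|---|
| 0 | 75% | 65.7-82.5% |
| 3 | 72% | 62.5-79.9% |
| 5 | 70% | 60.4-78.1% |
| 8 | 67% | 57.3-75.4% |

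For r = 5: centre = 0.719208/1.038416 = 0.6926; half-width = 1.96·√(0.0021 + 0.000096)/1.038416 = 0.0885.

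The table counts re-operated *responders*. If 3 to 8 patients were re-operated and all reached the MCID, the drop is 3 to 8 points. If half did, it is 1.5 to 4 points. If nobody was re-operated before the 12-month score, it is zero.

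**Step 4. Simple exclusion does not do the same job.** Assume 70 responders in 100, with 10 patients re-operated, of whom 5 are responders. Dropping the ten gives 65/90 = 72.2%, which is above the observed 70%. Counting them as non-responders gives 65/100 = 65%.

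**Step 5. Mean change and paired test.** No inequality like that in step 2 applies here. A score after re-operation may be better or worse than the rest of the sample, for instance worse if surgery came shortly before the visit.

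**The case against.** The strongest reply is that the rule is a coherent treatment-policy measure: each patient's status at 12 months compared with before surgery, whatever care followed. The hypothesis claims improvement over preoperative scores, not improvement net of later surgery. This is a legitimate choice, but the plan does not declare it, and it sits poorly with a purpose stated in terms of the device's performance. Keeping the observed-score rate alongside meets the objection.

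Several stronger readings are tempting and should not be drawn:

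- **That the plan labels a re-operated patient a success of the index procedure.** It does not. It speaks of per-patient clinical improvement and defines no composite success endpoint.
- **That the responder rate is the main statement of clinical benefit.** The listed secondary outcomes are the changes in VAS leg, VAS back and ODI. The responder proportions are a further summary with no threshold or decision rule attached.
- **That all the patient-reported results are biased in the device's favour.** That holds only for the responder rate, and only relative to counting re-operation as non-response.
- **That the failures are hidden.** Non-union, migration, loss of fixation, radiculopathy and adjacent segment disease are collected and reported as rates. Those rates are by event type, however, so a count of re-operations is not promised.

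It is also true that without a control arm no responder definition isolates the effect of the cage. The change proposed here removes one identifiable distortion and no more.

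A separate data processing plan is cited in Attachment A section 4.4 and is not among the documents. It is described there as governing data processing and management. Endpoint rules belong in sections 9.2 and 6.2, which are silent.

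**Conclusion.** The point holds for the secondary patient-reported outcomes. As written, a patient who had revision or additional lumbar surgery before the 12-month score can be counted as an MCID responder, and that score also enters the mean change and the paired test. The responder rate can be inflated by one point per re-operated responder per 100 patients. The direction for the mean change is not established.

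The true size cannot be obtained from the documents. The move from 75% to 70% rests on three assumptions: a 75% observed rate, five re-operated patients in 100, and all five reaching the MCID. The last is the extreme case. Even so, 70% lies inside the 65.7-82.5% interval around 75%. A reader might take a drop of several points as the expected effect; the documents support only the mechanism and the per-patient arithmetic. The fusion outcome and the target of 118 are not touched. The change is worth making because it is cheap and because the rule should be fixed before responder rates are tabulated.

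**What to change.** In section 9.2 and Attachment A section 6.2:

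1. Report each MCID responder rate with patients who had post-operative revision or additional lumbar surgery before the 12-month score counted as non-responders. Show the observed-score rate beside it.
2. Identify these patients from action codes 3 and 4 in the Post-Operative Adverse Event Log only. The Intra-Operative log carries the same codes, and an entry there could concern extra surgery at the index operation itself.
3. Take the date and anatomical site of the re-operation from the chart. The log holds the onset and resolution dates of the event, but neither the date nor the site of the re-operation.
4. State how many paired 12-month scores, for each instrument, were taken after re-operation.
5. Repeat the mean-change summaries and paired tests without those scores as a sensitivity analysis. It should not replace the main summary, because it removes patients who needed a second operation.

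The cost is a few sentences, one extra table row per instrument, the sensitivity summaries, and minor extra chart abstraction for the re-operated patients. The responder rate may come out slightly less favourable. The sample size does not change.
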